APPENDIX A: SCHEDULE OF EVENTS

Building A – Tailored intervention first followed by campaign

Visit	Activity	Timing	Compensation
1. – T0	Survey – 1 hour	Entry to study	\$15.00
2. – T0	Clinical assessment, skills assessment – 20 minutes	Entry to study	\$15.00
3.	Tailored educational session 45 min – 1 hour	Up to 45 days post T0	None
4. – T1	Survey – 1 hour	1-3 months after educational session	\$15.00
5. – T1	Clinical assessment, skills assessment – 20 minutes	1-3 months after educational session	\$15.00
	3 Campaign Events/Oral health fairs – 2-3 hours each	2-5 months after T1	None
6. – T2	Survey– 1 hour	1-3 months after campaigns	\$15.00
7. – T2	Clinical assessment, skills assessment – 20 minutes	1-3 months after campaigns	\$15.00
8. – T3	Clinical assessment, skills assessment, GOHAI – 20 minutes	6-7 months after T2	\$20.00

12/14/2010

Building B – Campaigns first followed by tailored intervention first

Visit	Activity	Timing	Compensation
1. – T0	Survey – 1 hour	Entry to study	\$15.00
2. – T0	Clinical assessment , skills assessment – 20 minutes	Entry to study	\$15.00
	3 Campaign Events/Oral health fairs – 2-3 hours total	3-6 months after study entry	None
3. – T1	Survey– 1 hour	1- 3 months after campaigns completed	\$15.00
4. – T1	Clinical assessment , skills assessment – 20 minutes	1- 3 months after campaigns completed	\$15.00
5.	Tailored educational session 45 min. to 1 hour	Up to 45 days after T1	None
6. – T2	Survey– 1 hour	1-3 months after educational session	\$15.00
7. – T2	Clinical assessment, skills assessment – 20 minutes	1-3 months after educational session	\$15.00
8. – T3	Clinical assessment, skills assessment, GOHAI – 20 minutes	6-7 months after T2	\$20.00

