5.3 Strategies for Recruitment and Retention

During the first five months of each full intervention cycle 120 residents will be enrolled into the study, 60 in each condition to which their building has been randomly assigned. Research team members will introduce the study in each of the buildings to tenants' associations and onsite managers, soliciting their support for the study. They will conduct 2 presentations 2 weeks apart to inform residents of the study, recruit and enroll potential participants, and within 2 – 3 days schedule appointments to conduct baseline surveys and clinical assessments. Participants will be recruited, enrolled, consented and scheduled for surveys during the first five months regardless of sequence of intervention. Thus, the timing of all surveys and clinical assessments will be the same for both buildings. Research team members will establish a base in a central location in each of the buildings from which to continue recruiting, place informational posters in elevators and in other public locations, actively recruit through engaging people in public spaces, and organizing weekly activities such as bingo games through which recruitment and enrolment will occur. These strategies were very successful in the pilot study. At the same time, 5 - 10 resident volunteers will be invited to join a campaign committee to co-plan and facilitate three building-wide campaigns. Based on prior experience we estimate overall attrition to be approximately 25%.

Retention. Retention in the study will be accomplished:

- a) Through continuous presence in the intervention buildings
- b) Repeated contact through face to face communication and fliers with intervention participants throughout the delivery of each component,
- c) Active telephone and mail reminders in advance of scheduled appointments for surveys, clinical assessments, individual AMI-PM session and campaigns.

We will retain people in the study who, for medical or travel reasons, missed no more than one intervention, one assessment time point, or one intervention and one assessment time point.

Based on prior studies in senior housing, these methods have demonstrated intervention acceptability and are expected to result in almost 100% retention among those residents who are not ill, have not passed away, and have not moved elsewhere.

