6 STUDY INTERVENTION

Study Behavioral or Social Intervention(s) Description

Conceptual Framework

The conceptual framework for the study intervention based on an adaptation of Fishbein's MI model utilized in our pilot study is summarized in Figure 1. Moderators include: demographic variables, subjective health, activities of daily living (ADLs), symptoms of depression (CES-D), self-assessed oral health; Intervention variables are the following: cognitive behavioral mediators to be targeted by the intervention include oral health knowledge, oral health beliefs, oral health social support, self-reported oral hygiene behaviors; oral health self-management worries and fears, oral health norms and behavioral intentions. Primary outcome variables are the Plaque Score and Gingival Index. Oral Health Quality of Life is a secondary outcome.

Intervention Implementation

The intervention we are proposing is a tailored bi-level intervention with two components, an individual level component (component A) with tailored messages based on performance on clinical assessment results, ADLs and cognitive domains in the survey delivered through adapted motivational interviewing with practice to mastery (AMI-PM); and a building level campaign (component B) open to all building residents that includes building tailored messages based on cognitive domains and skills reinforcement through Practice to Mastery.

Tailored Individual Level Intervention through Adapted Motivational Interviewing: (Component A).

The individually tailored individual-level intervention is approximately 45 minutes, and will take place within 45 days of administration of the baseline survey and clinical assessment in Condition A buildings, and within 45 days of administration of the T1 survey and clinical assessment in Condition B buildings. Trained project staff will administer the intervention. Interventionists will make appointments with residents who have completed the baseline assessment, review assessment materials and construct the intervention checklist specific to that individual based on findings from the survey and the clinical assessment. They will conduct the intervention either in the privacy of the resident's apartment or in a private location within the building.

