^{**}Sensory impairment (visual or aural) codes: 4 = no sensory problem apparent for either; 3 = some visual or aural impairment; request for repetition of instructions and vocabulary; some difficulty with print size (not related to literacy); 2 = has difficulty hearing and/or can't see instructions at all; 1 = cannot hear sufficiently to respond to a question properly (not a language problem), and/or cannot see enough to recognize the pattern of plaque on teeth (not a comprehension problem).

¹We are measuring oral hygiene skills at T0 – T3, but do not intend to use the results as a mediating measure in accordance with an NIDCR approved request to remove the OH skills assessment as a mediating measure from the study. It was never used as an outcome, but only as a mediator.

12/1/2010

The group level oral health campaign involves volunteer residents as partners in the development of the fairs designed to delivery oral hygiene self-management messages based on the cognitive domains, ADL related problems in brushing and flossing, and brushing and flossing skills, and offer an opportunity to practice brushing and flossing on a mouth model to mastery. To fulfill the requirements of the campaign component of the study (CA), up to three health fairs will be implemented over approximately a three month period. CA+PM procedures include the following:

Identification, Training and Preparation of Pro-GOH Campaign Volunteers. Throughout Condition 1 (AMI-PM+CA+PM) and in the first month of Condition 2 (CA+PM+ AMI-PM) the study team will recruit 5-10 building residents to facilitate the group intervention. The committee will include building residents as role models who are broadly representative of the composition of the building by age, ethnicity, gender, ability and language. All committees will have bilingual (English/Spanish) capacity. Once recruited, consented and enrolled, committee members will meet with study trainers for 2-hour sessions twice a week, for a minimum five to six week period, to learn how to implement pro-oral health campaigns, to plan for each fair and to work with study interventionists to develop campaign materials. The Pro-GOH campaign events follow primary communications principles:

- a) Message redundancy: same message delivered through different materials (at least 4 different types of materials in English and Spanish),
- b) Multiple channels (messages delivered through oral, visual, written and practice means)

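### Fairs are building-wide but timed from each person's own entry or T1, so with five-month enrolment they can precede late enrollees' T0 or T1

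*Combined protocol and SAP*

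**What the plan says.** - **Enrolment and T0.** Section 5.3: "During the first five months of each full intervention cycle 120 residents will be enrolled into the study". Staff are to "within 2 – 3 days schedule appointments to conduct baseline surveys and clinical assessments", and Appendix A places T0 at entry, so baselines are spread over the same five months.
- **Fairs.** Section 6 describes "a building level campaign (component B) open to all building residents" and says that "up to three health fairs will be implemented over approximately a three month period". Each building thus has one set of fair dates, shared by everyone.
- **Condition 2 (campaign first).** Appendix A places the fairs "3-6 months after study entry", after T0 and before T1.
- **Condition 1 (AMI-PM first).** The individual session is "Up to 45 days post T0", T1 is "1-3 months after educational session", and the fairs are "2-5 months after T1".
- **Analysis.** Section 12.1 states Hypothesis 1 as AMI-PM against CA+PM on clinical outcomes at T1. Section 12.2 powers the trial on this first period, and Section 12.4 analyses it as a parallel two-arm comparison. The mediator models in Section 12.4 use change from T0.
- **End point of follow-up.** The Protocol Summary puts T3 at 16-18 months after entry; Appendix A puts it 6-7 months after T2.

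**The concern.** The fair windows are counted from personal dates, but the fairs have building dates. When personal dates differ by up to five months and each window is three months wide, one set of fairs cannot suit everyone. A site that schedules for its early enrollees may hold a fair before its late enrollees have been assessed. Because the fairs are open to all residents, a person can attend one before enrolling.

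Two assessments are exposed. In Condition 1, a T1 taken after a fair measures AMI-PM plus some campaign rather than AMI-PM alone. In Condition 2, a T0 taken after a fair is no longer free of intervention. No rule in the available text requires all of a building's T0s (Condition 2) or T1s (Condition 1) to be complete before its first fair. Section 5.3 says that assessment timing is the same in both buildings of a pair, but this sets no fair date.

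**Working it through.** Time is in months from the start of enrolment in a building. Entry *e* runs from 0 to 5 (Section 5.3). All windows come from Appendix A, with 45 days taken as 1.5 months. The plan gives no figure of its own to reproduce.

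**Condition 2, personal anchor.** Fair window = [e + 3, e + 6].
- First enrollee (e = 0): 3 to 6. Last enrollee (e = 5): 8 to 11. The gap is 8 − 6 = 2 months, so no date fits both.
- A campaign spanning *s* months fits people whose entries differ by at most 3 − s months. Under uniform entry (assumed), the largest share with every fair in window is (3 − s)/5: 60% for a single date, and 40%, 20% and 0% for campaigns of 1, 2 and 3 months.

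**Condition 2, building anchor.** If study entry means the building's start, the fairs fall in months 3-6 for everyone. Enrolment and T0 run to month 5, so months 3-5 still overlap.

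**Condition 2, T0s taken after the first fair.** With the first fair at month *f* and uniform entry, the share is (5 − f)/5 for f up to 5.
- f = 3: 2/5 = 40%, or 24 of 60.
- f = 4: 1/5 = 20%, or 12 of 60.
- f = 5 or later: none.

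Early fairs are practicable. Section 6 recruits the Condition 2 committee in the first month and trains it for at least five to six weeks.

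**Condition 1.** T1 = e + (0 to 1.5) + (1 to 3) = e + 1 to e + 4.5. Fair window = [T1 + 2, T1 + 5].
- T1 falls in months 1-4.5 for the first enrollee and 6-9.5 for the last.
- With the same lag L for both, the windows are [L + 2, L + 5] and [L + 7, L + 10], again 2 months apart.
- With the most favourable lags (first T1 at 4.5, last at 6), the windows are 6.5-9.5 and 8-11. They overlap at 8-9.5, which is 1.5 months: enough for one fair or a short campaign, but not for about three months of fairs.
- Fairs timed to a T1 at month 1 fall in months 3-6, before or at the earliest possible T1 of the last enrollee (month 6).

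**Room for a remedy: first enrollee's T3, with a three-month campaign and minimum later intervals.**
- Condition 2: T3 ≥ f + 3 (campaign) + 1 (to T1) + 0 (to session) + 1 (to T2) + 6 (to T3) = f + 11. T3 by month 18 needs f ≤ 7, so a start in months 5-7 works. Restarting the three-month wait at the last T0 gives f ≥ 8 and T3 ≥ 19.
- Condition 1: T3 ≥ f + 3 + 1 + 6 = f + 10, so f ≤ 8. The last T1 can be no earlier than month 6. Restarting the two-month wait there gives f = 8 and T3 = 18 exactly, with no slack.

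**The case against.** Four points can fairly be made for the plan.

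1. **Order is not unregulated.** Appendix A lists T0 before the Condition 2 fairs and T1 before the Condition 1 fairs, so an out-of-order assessment departs from that participant's schedule. A site could preserve order by letting early enrollees run past their window. This stands: a reader might infer that reversal is inevitable, and it is not. A first fair at month 5 or 6 lies within the first enrollee's Condition 2 window and follows all enrolment. But the plan does not say whether window or order gives way, and a three-month campaign starting then runs past month 6.
2. **Condition 1 has a feasible date.** A reader might infer that no date works in either condition. The 8-9.5 overlap contradicts that for Condition 1, although only with early T1s delayed, late ones hurried and a campaign of at most 1.5 months.
3. **T0 may not enter Hypothesis 1.** The plan powers a two-group t-test and does not say that the T1 comparison uses change scores. In a comparison of T1 levels, a post-fair T0 does no harm. This stands. The Condition 1 route needs no such condition.
4. **The gap may be closed elsewhere.** The study schematic is not in the available text, and Section 7.2 refers baseline detail partly to a manual of procedures that is not included. The absence of an ordering rule is established only for the text at hand.

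The size is also easy to overstate. At mid-window lags in Condition 1 (session 0.75 month after T0, T1 two months later), the first enrollee's fair window is 4.75-7.75. Under uniform entry the share of T1s after the first fair is 60% if it is held on the opening day, 30% at mid-window (6.25) and 0% at the close. No single figure is supported. Nor can a proportion of campaign effect absorbed into baseline be given, because fair dates, effect per fair and attendance before enrolment are not documented.

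**Conclusion.** The concern holds as a schedule that cannot be met for everyone and that permits contamination. In Condition 2 the conflict is outright on the personal reading, and overlap with T0 collection remains on the building reading. In Condition 1 the full campaign does not fit both extremes even with the best lags.

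A post-fair T1 in Condition 1 directly affects the comparison on which the trial is powered. A post-fair T0 in Condition 2 affects analyses that use change or baseline adjustment, including the mediator models. If the fairs work, the first adds campaign benefit to the AMI-PM arm and the second understates improvement in the campaign arm. Both favour AMI-PM, the direction that Hypothesis 1 predicts.

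The Condition 2 shares of 40%, 20% and 0% rest on uniform enrolment and on the date of the first fair. They count assessments out of order, not people exposed; exposure also depends on attendance.

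**What to change.** - **Ordering rule.** In Appendix A and Section 5.3, replace the personal anchor for the fairs with a building-level rule: the first fair is held only after that building's last T0 (Condition 2) or last T1 (Condition 1).
- **Reconcile the windows.** Revise the fair-window lengths together with the enrolment period and T3 at 16-18 months, rather than restarting the full 3-6 or 2-5 month wait at the milestone. For example, a three-month Condition 2 campaign starting at about months 5-7 still allows the first enrollee's T3 by month 18 at minimum later intervals. In Condition 1 the same arithmetic needs the campaign to start by month 8, so the last T1 must be done by then.
- **Flag and repeat.** Using assessment dates and the fair dates recorded from the passports (Sections 13 and 16.3), flag every Condition 2 T0 and Condition 1 T1 taken after the building's first fair. Repeat the T1 comparison and the change-from-T0 analyses without those records. This can be done even for cycles already under way.

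The cost is protocol wording, scheduling and one sensitivity analysis. Early enrollees will have a longer and more variable gap between T0 or T1 and the fairs, and there will be less slack before T3.
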